2.4.5 Analyses of safety data

The summary of safety results will be presented by treatment group, for both the overall population and separately for each ethnic/race subgroup, for the 26-week randomized treatment period, unless specified otherwise.

All safety analyses will be performed on the safety population using the following common rules:

The “observation period” defined in [Section 2.1.4](#) is applicable in all safety analyses for the classification of AEs, determination of treatment-emergent Potentially Clinically Significant Abnormality (PCSA) values and the last on-treatment value for the laboratory, vital sign and ECG.

General common rules

All safety analyses will be performed on the safety population as defined in [Section 2.3.2](#), unless otherwise specified, using the following common rules:

- Safety data in patients who do not belong to the safety population (e.g., exposed but not randomized) will be listed separately
- The baseline value is defined as the last available value before the first dose of IMP
- PCSA values are defined as abnormal values considered medically important by the Sponsor according to predefined criteria/thresholds based on literature review and defined by the Sponsor for clinical laboratory tests, vital signs, and ECG. PCSA criteria will determine which patients had at least 1 PCSA during the treatment-emergent adverse event period, taking into account all evaluations performed during the treatment-emergent adverse event period, including nonscheduled or repeated evaluations. The number of all such patients will be the numerator for the treatment emergent PCSA percentage
- The treatment-emergent PCSA denominator by group for a given parameter will be based on the number of patients assessed for that given parameter in the treatment-emergent adverse event period by treatment group on the safety population.
- For laboratory parameters cited in the protocol as efficacy endpoints (including HbA1c and plasma glucose etc.), PCSA summaries will not be provided. These parameters will be summarized in [Section 2.4.4](#).
- For quantitative safety parameters based on central laboratory/reading measurements, descriptive statistics will be used to summarize results and change from baseline values by visit and treatment group for the entire 26-week treatment period only. Summaries will include the last on-treatment value. The last on-treatment value is commonly defined as the value collected at the same day/time of the last administration of IMP. If this value is

missing, this last on-treatment value will be the closest value prior to the last dose administration of IMP during the entire 26-week treatment period.

- The analysis of the safety variables will be essentially descriptive and no systematic testing is planned. Relative risks versus Lantus and their 95% confidence intervals may be provided, if relevant

2.4.5.1 Hypoglycemia

Analyses of hypoglycemia will be performed on the TEAE period as defined in [Section 2.1.4](#). Hypoglycemia will be classified as severe hypoglycemia, documented hypoglycemia (blood glucose ≤ 70 mg/dL and < 54 mg/dL), probable symptomatic hypoglycemia or pseudo hypoglycemia.

The number (%) of patients with at least 1 hypoglycemia, severe hypoglycemia and documented hypoglycemia (blood glucose ≤ 70 mg/dL and < 54 mg/dL), probable symptomatic hypoglycemia or pseudo hypoglycemia will be summarized respectively by treatment group during the TEAE period, as well as the incidence rate in patient years. Two types of incidence rates will be presented: the number of patients with at least 1 event per patient-year (calculated as the number of patients with at least 1 event / total exposure in patient-year), and the number of events per patient-year (calculated as the total number of events / total exposure in patient-years). Note: here exposure (in days) is the duration of TEAE period, i.e., duration of IMP treatment in days +1 (see [Section 2.1.4](#)).

A KM curve will also be provided by treatment group for the time to first severe hypoglycemia or documented hypoglycemia during the TEAE period for the entire 26-week treatment period only.

A listing of patients for all events reported on the dedicated e-CRF “Hypoglycemic event information” page will be provided with each category flagged (i.e., severe hypoglycemia, documented hypoglycemia, probable symptomatic hypoglycemia and pseudo hypoglycemia).

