1 OVERVIEW AND INVESTIGATIONAL PLAN

1.1 STUDY DESIGN AND RANDOMIZATION

This study is an open-label, 1:1 randomized, active-controlled, 26-week duration, parallel-group, multicenter, US-only, Phase 3b study to compare the efficacy and safety of Soliqua 100/33 with Lantus overall and in ethnically/racially diverse groups with T2DM inadequately controlled on basal insulin and 1 or 2 OAD agents. The patients will be randomized according to their self-reported ethnicity/race (i.e., Hispanics of any race, non-Hispanic black/African Americans and non-Hispanic Asians). Additionally, to ensure a balanced IMP allocation, randomization will be stratified by their screening HbA1c value ($<8.5\%$ versus $\geq 8.5\%$), the background use of SGLT-2 inhibitors (yes/no) and the background use of SUs (yes/no). Patients will participate in 1 of 2 ways, either at a traditional 'brick & mortar' investigational site, or fully remotely through a virtual arrangement.

The study will consist of 3 periods:

- An up to 2-week screening period
- A 26-week open-label randomized treatment period: at the end of the screening period (Week 0, Visit 2) patients will be randomized to receive either Soliqua 100/33 or Lantus
- A 3-day post-treatment safety follow-up period (not required for patients who prematurely and permanently discontinued IMP administration but stayed in the study through Week 26; these patients should continue all study visits except for the follow-up visit).

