1.3 DETERMINATION OF SAMPLE SIZE

Due to difficulty in recruitment, it has been decided to terminate the trial early, leading to a total sample size of 240 patients (120 per treatment), for which efficacy and safety of Soliqua 100/33 and Lantus will be evaluated using descriptive statistics.

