2.4.3.1 Extent of investigational medicinal product exposure

The extent of IMP exposure will be assessed by the duration of IMP exposure.

Duration of IMP exposure is defined as last dose date of IMP – first dose date of IMP + 1 day, regardless of unplanned intermittent discontinuations (see [Section 2.5.3](#) for calculation in case of missing or incomplete data).

Duration of IMP exposure will be summarized descriptively as a quantitative variable (number of patients exposed, mean, SD, median, minimum, and maximum). In addition, duration of treatment exposure will also be summarized categorically by numbers and percentages for each of the following categories and cumulatively according to these categories:

- 1 to 28 days,
- 29 to 56 days,
- 57 to 84 days,
- 85 to 126 days,
- 127 to 168 days
- 169 to 175 days
- 176 to 182 days
- >182 days

Additionally, the cumulative duration of treatment exposure will be provided, defined as the sum of the duration of treatment exposure for all patients, and will be expressed in patient years.

Number and percentages of patients by final dose at the end of the treatment will also be presented by each treatment group.

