When a patient has more than 1 measurement from the central laboratory for the same laboratory parameter on the same date, the average of the measurements will be used. For the same laboratory parameter, if a patient has more than 1 measurement on different dates for the same scheduled visit, the value closest to the date of the visit will be used for the scheduled visit. When the values for the same scheduled visit are equidistant, the last value should be used for the scheduled visit. Similar rules will be applicable to a patient who has more than 1 set of measurements for the same vital sign parameter (i.e., SBP, DBP, or HR) on the same date.

26-week randomized treatment period

The 26-week randomized treatment period is the time from first administration of IMP to the last administration of IMP on or before Visit 19/Week 26 (or Day 182 if Visit 19/Week 26 date is missing). This is for defining EOT status at Week 26 and analyzing selected efficacy parameters during the 26-week randomized core treatment period.

TEAE period for the 26-week randomized treatment period

The TEAE period for 26-week randomized treatment period is (1) the time from the first administration of the IMP up to 10 days (1 day for hypoglycemia) after the last administration of IMP if the patient discontinued treatment on or before Visit 19/Week 26 (or Day 182 if Visit 19/Week 26 date is missing), or (2) the time from the first administration of the IMP to the administration at Visit 19/Week 26 (or Day 182 if Visit 19/Week 26 date is missing) if the patient remained treated beyond Visit 19/Week 26. This is for the purpose of safety analyses during the 26-week randomized treatment period.

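### The patient-level hypoglycemia rate keeps counting exposure after a patient's first event, so it understates the first-event incidence rate, materially only for common categories

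*SAP*

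**What the plan says.** SAP Section 2.4.5.1 states that "Two types of incidence rates will be presented". The patient-level rate is "calculated as the number of patients with at least 1 event / total exposure in patient-year". The event-level rate is "calculated as the total number of events / total exposure in patient-years". A note then defines exposure once for both: "here exposure (in days) is the duration of TEAE period, i.e., duration of IMP treatment in days +1". Nothing in it stops the clock at a first event.

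Section 2.4.3.1 runs the duration of treatment from first to last dose, "regardless of unplanned intermittent discontinuations". For a patient who completes treatment the period is 26 weeks; Section 2.5.3 uses Day 182 as the default end.

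Section 2.4.5.1 also plans the number and percentage of patients in each hypoglycemia category, a Kaplan-Meier curve of time to first severe or documented hypoglycemia, and a listing of all events. Section 2.4.5 describes the safety analysis as essentially descriptive, without systematic testing, and presents safety results overall and by ethnic/racial subgroup.

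**The concern.** The two rates share a denominator that suits only one of them. When all events are counted, a patient stays at risk of adding to the numerator for the whole TEAE period, so total exposure is correct. When patients are counted, someone who has had an event can add nothing more, yet the remaining exposure still goes into the denominator. The result is neither a first-event incidence rate nor an event rate, although the SAP calls it an incidence rate.

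Hypoglycemia has its own analysis section in this comparison of two insulin-containing regimens. With no formal testing left in the plan, readers will judge from the descriptive tables, including those by subgroup. A tabulated rate per patient-year is naturally read as an incidence rate, and for common categories it could be well below one.

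**Working it through.** The SAP states no hypoglycemia rate, so there is no figure to reproduce. The check compares the SAP formula with the same numerator over time at risk.

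**Inputs from the SAP**
- Patient-level rate and exposure: Section 2.4.5.1, as quoted above.
- Duration: a "open-label, 1:1 randomized, active-controlled, 26-week duration" study (Section 1.1). Treatment of 182 days plus 1 day under the exposure note gives T = 183/365.25 = 0.501 years.
- Size: 120 patients per arm (Section 1.3), so 120 × 0.501 = 60.1 patient-years per arm if all complete.

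**Assumptions, not in the SAP**
- The proportion p of patients with at least one event, shown as a range.
- A constant first-event hazard and a common T.

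**Step 1: direction, with no distributional assumption.** Let patient i have TEAE duration Tᵢ and time to first event Xᵢ. The SAP denominator is ΣTᵢ and time at risk is Σmin(Xᵢ, Tᵢ). The first is larger as soon as one patient has follow-up after a first event. The numerators are equal, so the SAP rate is the lower one.

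**Step 2: size within an arm.** SAP rate = p/T. First-event rate = −ln(1−p)/T. Shortfall = 1 − p/[−ln(1−p)], which does not depend on T.

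| p | SAP rate (per patient-year) | First-event rate | Shortfall |
|---|---|---|---|
| 2% | 0.040 | 0.040 | 1.0% |
| 10% | 0.200 | 0.210 | 5.1% |
| 25% | 0.499 | 0.574 | 13.1% |
| 40% | 0.798 | 1.020 | 21.7% |
| 50% | 0.998 | 1.383 | 27.9% |
| 60% | 1.198 | 1.829 | 34.5% |

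For p = 50% in one arm, 60 patients have an event. The SAP divides by 60.1 patient-years and gets 0.998. Time at risk is 60/1.383 = 43.4 patient-years, so about 16.8 patient-years of the denominator fall after first events.

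**Step 3: contrast between arms, equal exposure.** T cancels, so the SAP rate ratio is p₁/p₂ and the first-event rate ratio is ln(1−p₁)/ln(1−p₂).

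| p₁ versus p₂ | SAP ratio | First-event ratio | SAP difference | First-event difference |
|---|---|---|---|---|
| 2% versus 1% | 2.00 | 2.01 | 0.02 | 0.02 |
| 20% versus 10% | 2.00 | 2.12 | 0.20 | 0.24 |
| 40% versus 25% | 1.60 | 1.78 | 0.30 | 0.45 |
| 60% versus 40% | 1.50 | 1.79 | 0.40 | 0.81 |

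**Step 4: sensitivity.** With patient-to-patient variation in hazard (gamma frailty, shape 1, mean hazards 2.0 and 1.2 per year, equal exposure), the SAP ratio is 1.33 and the time-at-risk ratio 1.50, so the direction is the same. With constant hazards of 1.5 and 1.2 per year the first-event ratio is 1.25. Using SAP rate = (1−e^(−λT))/T:
- Higher-hazard arm exposed 160 days, other arm 183: SAP ratio 1.22, still closer to 1.
- Higher-hazard arm exposed 120 days, other arm 183: rates 1.184 and 0.902, SAP ratio 1.31, now further from 1.

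**The case against.** The strongest reply is that the SAP defines this quantity openly and never calls it a first-event hazard. With equal exposure its ratio between arms is a ratio of proportions, which is a legitimate risk ratio. On this view 1.50 and 1.79 are different effect measures, not a wrong and a right one. The SAP plans no ratio of these rates and tests nothing; Section 2.4.5 mentions only optional relative risks. The percentage, the event-level rate, the Kaplan-Meier curve and the listing all appear beside it.

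Much of this stands and limits the severity. It does not remove the point. The SAP labels the figure an incidence rate per patient-year, and the denominator does not match the numerator. If the quantity is in effect a rescaled proportion, it adds almost nothing to the percentage in the same paragraph. The Kaplan-Meier curve handles time at risk properly, but only for severe or documented hypoglycemia. Any, probable symptomatic and pseudo hypoglycemia have no such summary.

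A reader might also infer that the formula always favours the arm with more hypoglycemia and always pulls the comparison towards no difference. The SAP does not support that. Such a pull needs broadly similar exposure in the two arms. A 1:1, 26-week design makes that the natural starting assumption, but early stopping can undo it, and the 120-day case above reverses the direction.

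**Conclusion.** The point holds, with modest severity. The patient-level rate understates the first-event incidence rate whenever exposure continues after a first event; that part is arithmetic. The size depends on event frequencies that the SAP does not give and, in these figures, on a constant hazard. It is about 1% or less where 2% or fewer patients are affected, as may be so for severe events. It rises from 13% at 25% affected to 35% at 60%, which would matter for any hypoglycemia or the 70 mg/dL category if these are that common.

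The effect on the between-arm contrast is conditional. With similar exposure the stated ratio collapses to the ratio of proportions; with a large imbalance it can move either way. No planned test or formal conclusion is affected. What is at stake is whether a descriptive safety figure means what its label says.

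**What to change.** In Section 2.4.5.1, for the patient-level rate only, define exposure as the time from first IMP administration to the first event of the category being tabulated, or to the end of the TEAE period for patients without such an event. Keep total TEAE-period exposure for the event-level rate. An acceptable alternative is to drop the patient-level rate and rely on the percentage, the event-level rate and the Kaplan-Meier curve.

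The cost is one sentence in the SAP and one time-to-first-event variable per category: any, severe, ≤70 mg/dL, <54 mg/dL, probable symptomatic and pseudo hypoglycemia. The planned Kaplan-Meier curve already needs this derivation only for severe or documented hypoglycemia, so the other categories are additional but small work from the same eCRF page. No new data are required.

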2.4.5.2 Analyses of adverse events

Generalities

The primary focus of adverse event reporting will be on treatment-emergent adverse events. Pre-treatment and post-treatment adverse events will be described separately.

If an adverse event date/time of onset (occurrence, worsening, or becoming serious) is incomplete, an imputation algorithm will be used to classify the adverse event as pre-treatment, treatment-emergent, or post-treatment. The algorithm for imputing date/time of onset will be conservative and will classify an adverse event as treatment emergent unless there is definitive information to determine it is pre-treatment or post-treatment. Details on classification of adverse events with missing or partial onset dates are provided in [Section 2.5.3](#).

Adverse event incidence tables will be presented by SOC, HLG, HLT, and PT, sorted by the internationally agreed order for SOCs and alphabetic order for HLG, HLT and PT within a SOC, the number (n) and percentage (%) of patients experiencing an adverse event. Multiple occurrences of the same event in the same patient will be counted only once in the tables within a treatment phase. The denominator for computation of percentages is the safety population within each treatment group.

Sorting within tables ensures the same presentation for the set of all adverse events within the observation period (pre-treatment, treatment-emergent, and post-treatment). For that purpose, the table of all treatment-emergent adverse events presented by primary SOC and PT (sorted by the internationally agreed SOC order and decreasing frequency of PTs within SOCs in the Soliqua 100/33 group) will define the presentation order for all other similar tables unless otherwise specified. In case of equal frequency regarding PTs, alphabetical order will be used.

Analysis of all treatment-emergent adverse events

The following treatment-emergent adverse event summaries will be generated during the 26-week randomized treatment period for the safety population.

- Overview of treatment-emergent adverse events, summarizing number (%) of patients with any
 - TEAE
 - Serious TEAE
 - TEAE leading to death
 - TEAE leading to permanent treatment discontinuation
- All treatment-emergent adverse events by primary SOC, showing number (%) of patients with at least 1 treatment-emergent adverse event, sorted by internationally agreed order of primary system organ class
- All adverse events for the whole on-study period (on-treatment and post-treatment periods) by primary SOC, showing number (%) of patients with at least 1 adverse event during the on-study period, sorted by internationally agreed order of primary system organ class
- All treatment-emergent adverse event by primary SOC, HLG, HLT, and PT, showing number (%) of patients with at least 1 treatment-emergent adverse event sorted by the SOC internationally agreed order. The other levels (HLG, HLT, PT) will be presented in alphabetical order
- Number (%) of patients experiencing TEAE(s) presented by PT, sorted by decreasing incidence of PT in the Soliqua 100/33 group
- All treatment-emergent adverse events by primary SOC and PT, showing the number (%) of patients with at least 1 treatment-emergent adverse event, sorted by the internationally agreed SOC order and by decreasing incidence of PTs within each SOC in the Soliqua 100/33 group. This sorting order will be applied to all other similar tables, unless otherwise specified

- All treatment-emergent adverse events regardless of relationship and related to IMP by primary SOC, HLGT, HLT and PT, showing the number (%) of patients with at least 1 treatment-emergent adverse event, sorted by the internationally agreed SOC order. The other levels (HLGT, HLT, PT) will be presented in alphabetical order
- All treatment-emergent adverse events by maximal severity, presented by primary SOC and PT, showing the number (%) of patients with at least 1 treatment-emergent adverse event by severity (i.e., mild, moderate, or severe), sorted by the sorting order defined above
- Common TEAEs (PTs with an incidence $\geq 1\%$ in any treatment group) by primary SOC, HLGT, HLT, and PT, sorted by internationally agreed order of SOCs. The other levels (HLGT, HLT, PT) will be presented in alphabetic order.
- Common TEAEs (PTs with an incidence $\geq 1\%$ in any treatment group) will be provided as appropriate by primary SOC, HLGT, HLT, and PT and by demographic factors including gender (Male, Female), age group (<50, ≥ 50 to <65, ≥ 65 years of age), race (White, Black or African American, Asian, other). SOC will be sorted by internationally agreed order and the other levels (HLGT, HLT, PT) in alphabetic order.

Analysis of all treatment emergent serious adverse event(s)

- All treatment-emergent serious adverse events by primary SOC, HLGT, HLT, and PT, showing the number (%) of patients with at least 1 serious treatment-emergent adverse event, sorted by the internationally agreed SOC order. The other levels (HLGT, HLT, PT) will be presented in alphabetical order
- All treatment-emergent serious adverse events regardless of relationship and related to IMP, by primary SOC, HLGT, HLT, and PT, showing the number (%) of patients with at least 1 treatment-emergent serious adverse event, sorted by the internationally agreed SOC order. The other levels (HLGT, HLT, PT) will be presented in alphabetical order

Analysis of all treatment-emergent adverse event(s) leading to treatment discontinuation

- All treatment-emergent adverse events leading to treatment discontinuation, by primary SOC, HLGT, HLT, and PT, showing the number (%) of patients sorted by the internationally agreed SOC order. The other levels (HLGT, HLT, PT) will be presented in alphabetical order

Analysis of adverse events of special interest

- Serious allergic/hypersensitivity reactions, pregnancy and overdose for the combined on-treatment and post-treatment period will be included in overall AE summaries if any are reported. ALT increase $>3 \times$ ULN for the TEAE period is included in laboratory PCSA summary and listed in the PCSA listing which will include both the on-treatment and post-treatment periods.

Gastrointestinal adverse events

- The number (%) of patients with events reported on the AE form for gastrointestinal adverse events will be summarized by PT for each treatment group.

Analysis of pre-treatment and post-treatment adverse events

- All pre-treatment adverse events by primary SOC and PT, showing the number (%) of patients with at least 1 pre-treatment adverse event, sorted by the internationally agreed SOC order and decreasing incidence of PTs within each SOC in the Soliqua 100/33 group
- All posttreatment adverse events by primary SOC and PT, showing the number (%) of patients with at least 1 posttreatment adverse event, sorted by the internationally agreed SOC order and decreasing incidence of PTs within each SOC in the Soliqua 100/33 group

Listings

Supportive AE listings will be provided for all AEs, SAEs, AEs leading to treatment discontinuation and/or death, and EOSI as appropriate. Listing of all AEs, SAEs and AEs leading to treatment discontinuation and/or death, sorted by treatment, patient identification and onset date, will include at least the following information: treatment, patient identification, country, age, gender, race, BMI, primary SOC, PT, reported term, onset date, study day (relative day to the start date of IMP treatment), AE duration, duration of exposure, intensity, corrective treatment, action taken with IMP, date of treatment discontinuation (if relevant), relationship to IMP, outcome, date of death (if any), seriousness, seriousness criteria, and AE status (“Pre” for a pre-treatment AE; “T” for a TEAE; and “Post” for an on-study post-treatment AE).

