2.1.4 Safety endpoints

The safety analysis will be based on the reported adverse events, hypoglycemia, and other safety information, such as clinical laboratory data, and vital signs, etc.

Observation period

The observation period for safety data will be divided into 3 segments:

- The pre-treatment period is defined as the time between the date of signing of the informed consent (inclusive) and the first injection of IMP (exclusive),
- The on-treatment period is defined as the time from the first injection of IMP (inclusive) up to and including 3 days after the last injection of IMP (treatment-emergent AE [TEAE] period),
- The post-treatment period is defined as the time starting 4 days after last injection of IMP (after the TEAE period).

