2.1.4.2 Adverse events variables

Adverse event observation period

- The pre-treatment period is defined as the time between the date of signing of the informed consent and the first injection of IMP,
- The on-treatment period is defined as the time from the first injection of IMP up to and including 3 days after the last injection of IMP (treatment-emergent AE [TEAE] period),
- The post-treatment period is defined as the time starting 4 days after last injection of IMP (after the TEAE period).

All adverse events (including SAE, AESI) will be coded to a lower-level term (LLT), preferred term (PT), high-level term (HLT), high-level group term (HLGT), and associated primary system organ class (SOC) using the version of Medical Dictionary for Regulatory Activities (MedDRA) currently in effect at Sanofi at the time of database lock.

The occurrence of adverse events (including SAE and AESI) will be recorded from the time of signed informed consent until the end of the study or the resolution/stabilization of all SAE and AESI.

An adverse event of special interest (AESI) is an AE (serious or non-serious) of scientific and medical concern specific to the Sponsor’s product or program, for which ongoing monitoring and immediate notification by the Investigator to the Sponsor is required. Such events may require further investigation in order to characterize and understand them

AESI are listed below:

- ALT >3 x ULN;
- Serious allergic/hypersensitivity reactions;
- Pregnancy occurring in a female patient administered IMP/NIMP;
- Symptomatic overdose of IMP/NIMP

Table 3 - Criteria for AESI

AE Grouping	Criteria
AESI	
Serious allergic/hypersensitivity reactions	eCRF form “Hypersensitivity/Allergic”
Pregnancy	eCRF form “Pregnancy”
Symptomatic overdose	“Overdose of IMP” or “Overdose of NIMP” checked and “Symptomatic overdose” checked in eCRF form “Overdose”
ALT increase > 3X ULN	eCRF form “ALT increase”

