	1	1.2 ^b	2	3	4	5	6	7	8	9	10	11	12	13	14	15	16	17	18	19 ^c	19 + 3
VISIT ^a				☎	☎	☎	☎	☎		☎	☎	☎	☎	☎		☎		☎	☎		☎
WEEK	-2	-1	0	1	2	3	4	5	6	7	8	9	10	11	12	15	18	21	24	26	26+3 days
AEs/SAEs/AESIs/hypoglycemia collection	Continuously assessed and recorded throughout the study																				

☎ = Remote visit (telephone or videoconference); all other visits will be performed in person, at the site location, except for the patients that will be enrolled through the virtual site model, who will complete all study visits in a remote setting

- a. Screening period duration is of up to 2 weeks (i.e., it can be less than 2 weeks if all required procedures have been performed and patient's eligibility has been confirmed). Starting with Visit 3 through (and including) Visit 14, a ±2-day window, calculated relative to the Randomization Visit (Visit 2) is permitted; for Visits 15 through 18, a ±3-day window is permitted, while for Visit 19 a +3-day window is permitted. If a study visit is performed outside of the permitted window, the subsequent visits must be scheduled according to the original schedule (i.e., relative to the date of Visit 2, Randomization Visit). The date of the follow-up visit must be determined relative to the date of Visit 19. Additional remote visits should be scheduled as often as deemed necessary by the Investigator.
- b. Mandatory for all patients until at least 75 randomized patients per treatment/ethnicity/race group completed the test during the screening period; the visit can be performed any time prior to Visit 2, once the patient's eligibility based on Visit 1 criteria has been confirmed. Sponsor or designee will communicate when/if this evaluation is no longer required for study patients.
- c. In case of rescue therapy initiation or if IMP is being permanently discontinued, Week 26 (Visit 19) procedures should be performed before starting rescue therapy/IMP discontinuation; subsequently, patients should continue study treatment and all visits/procedures should be performed per protocol.
- d. Informed consent should be collected at Visit 1 only, before any other study procedures are performed (or when amendments to the consent are created by the Sponsor or designee).
- e. BMI will be calculated by the site at Visit 1 only using the following formula: $BMI = \text{weight (kg)} / (\text{height in m})^2$.
- f. Blood pressure and heart rate will be measured after 5 minutes rest in seated position.

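### Post-treatment AE percentages use the whole safety population, but completers have at most about one observed post-treatment day, so the figure largely tracks early stopping by arm

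*SAP*

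**What the plan says.** - **Denominator.** SAP Section 2.4.5.2, under Generalities: "The denominator for computation of percentages is the safety population within each treatment group". No exception by observation period follows.
- **Table affected.** The same section orders a separate post-treatment table: "All posttreatment adverse events by primary SOC and PT, showing the number (%) of patients with at least 1 posttreatment adverse event". It names no denominator of its own.
- **Period boundaries.** Section 2.1.4.2 runs the on-treatment period "up to and including 3 days after the last injection of IMP". Sections 2.1.4 and 2.1.4.2 both place the next period after that: "The post-treatment period is defined as the time starting 4 days after last injection of IMP".
- **Follow-up of completers.** Section 1.1 provides "A 3-day post-treatment safety follow-up period". Appendix C schedules the contact at 26 weeks + 3 days and adds: "The date of the follow-up visit must be determined relative to the date of Visit 19".
- **Follow-up of early stoppers.** Under Section 1.1, patients who stop IMP permanently but stay in the study skip the follow-up contact and keep their other visits through Week 26.
- **Contrast within the SAP.** Section 2.4.5 bases PCSA percentages on patients assessed in the period concerned, and Section 2.4.5.1 adds rates per patient-year for hypoglycemia.

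**The concern.** A percentage of patients with a post-treatment event reads as a frequency among people who could have had one. Under this schedule most of the denominator is hardly observed in that period, because the 3-day follow-up and the 3-day tail of the TEAE period cover nearly the same days. The numerator comes almost entirely from patients who stopped IMP early and were still followed. If more patients stop early and stay in one arm, that arm shows a higher post-treatment AE percentage even when the risk after stopping is the same.

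Section 2.4.5 asks for safety summaries overall and by ethnic/racial subgroup, where a handful of early stoppers can move the figure. It also leaves room for relative risks versus Lantus with 95% confidence intervals. On this table such a ratio would largely compare early stopping.

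**Working it through.** The SAP states no figure to reproduce on this point. The check is date arithmetic followed by a decomposition of the percentage.

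**1. Observed post-treatment days in a completer.** Let day 0 be the last injection.

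Post-treatment days = max(0, day of last contact − last TEAE day).

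| Last injection | Last contact | TEAE to day +3 (2.1.4, 2.1.4.2) | TEAE to day +10 (2.5.3) |
|---|---|---|---|
| Day of Visit 19 | day +3 | max(0, 3 − 3) = 0 | max(0, 3 − 10) = 0 |
| Day before Visit 19 | day +4 | max(0, 4 − 3) = 1 | max(0, 4 − 10) = 0 |

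The second row is realistic because Section 2.1.3 recognises a group dosing Lantus in the evening.

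**2. Observed post-treatment days in an early stopper.** Take a patient who stops on Day 60 and is followed to Day 182. With the 3-day window the TEAE period ends on Day 63, leaving Days 64 to 182, which is 119 days. With the 10-day window it ends on Day 70, leaving 182 − 70 = 112 days.

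**3. What the printed percentage measures.** Let q be the share of the arm's safety population that stopped IMP early and was followed past the TEAE period. Let p be the proportion of those patients with a post-treatment AE. Ignoring completers:

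printed % ≈ q × p.

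With the same p in both arms, the ratio between arms is the ratio of the q values.

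**4. Range.** The SAP gives neither q nor p, so all values below are assumptions.

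| q, arm A vs arm B | p in both arms | Printed % | Ratio | % among those followed |
|---|---|---|---|---|
| 10% vs 5% | 20% | 2.0 vs 1.0 | 2 | 20 vs 20 |
| 10% vs 5% | 40% | 4.0 vs 2.0 | 2 | 40 vs 40 |
| 10% vs 5% | 60% | 6.0 vs 3.0 | 2 | 60 vs 60 |
| 20% vs 10% | 40% | 8.0 vs 4.0 | 2 | 40 vs 40 |
| 20% vs 5% | 40% | 8.0 vs 2.0 | 4 | 40 vs 40 |
| 5% vs 5% | 40% | 2.0 vs 2.0 | 1 | 40 vs 40 |

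The last row shows that nothing is distorted between arms if early stopping is balanced.

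**5. Does one day per completer change this?** Suppose everyone who is not an early stopper has 1 observed post-treatment day, early stoppers have 90, and AEs arise at r per patient-year (all assumed). Then P(1 day) = 1 − exp(−r/365.25) and P(90 days) = 1 − exp(−90r/365.25). The early stoppers' share of patients with an event is q·P(90) / [q·P(90) + (1 − q)·P(1)].

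- r = 4, q = 5%: P(1) = 1.09%, P(90) = 62.7%; 3.13 / (3.13 + 1.03) = about 75%.
- r = 1, q = 20%: P(1) = 0.27%, P(90) = 21.8%; 4.37 / (4.37 + 0.22) = about 95%.

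Over r = 1, 2 or 4 and q = 5%, 10% or 20%, the share runs from about 75% to 95%.

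**The case against.** **The denominator is a stated choice.** The safety population is conventional, and the percentage correctly answers what share of treated patients had an AE recorded after treatment. That stands, and it suits the TEAE and whole on-study tables. It is a poor basis for a frequency, or for comparing arms, in a period most patients barely enter.

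**The alternative is not a randomized comparison.** Restricting to early stoppers conditions on something that happens after randomization. This also stands. A reader might infer that the restricted percentage gives the fair contrast between arms. It does not, and it does not equalise length of follow-up either.

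**A careless repair could do more harm.** Suppose the denominator were anyone with at least one day beyond the TEAE period. Lantus completers whose last dose was the evening before Visit 19 would enter, while completers dosed on the day of Visit 19 would not. Assume 24 vs 12 early stoppers per 120, 25% with an event in each arm (6 and 3 patients), and 50 such Lantus completers. The result is 6/24 = 25% against 3/62 = 4.8%, a ratio of about 5 where the present rule gives 5.0% vs 2.5%, a ratio of 2. The denominator must therefore be defined by early stopping.

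**Context is already planned.** Section 2.2 counts patients who stopped IMP and attended Week 26, and the AE listings carry a post-treatment status and the stop date. These help, but that count misses early stoppers who left the study before Week 26 yet after day +3, and no post-treatment person-time is planned.

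**Low stakes.** TEAEs are the stated primary focus, safety analysis is essentially descriptive, and relative risks are optional. This stands and limits the weight of the point.

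**Conclusion.** The point holds as a reporting weakness in one secondary, descriptive table. As planned, the percentage mixes how many patients stopped early and stayed under observation with how often those patients had an event. With equal risk the apparent ratio between arms equals the ratio of the early-stopper shares: 2 at 10% vs 5% or 20% vs 10%, and 4 at 20% vs 5%. Those shares are assumptions; the true size cannot be taken from the SAP.

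Three stronger readings are not supported:

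- A reader might infer that completers have no post-treatment observation at all. That is exact for a last dose on the day of Visit 19. A last dose one day earlier leaves one day under the 3-day window, and an SAE or AESI followed beyond study end could generate a later linked record.
- A reader might infer that only patients who stay to Week 26 contribute. Anyone who stops early and is observed past day +3 does.
- A reader might infer that the choice undermines what was added after FDA comments. Table 2 in Section 1.6 describes that addition as summaries over the whole on-study period, for which the safety population is a reasonable denominator.

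The conclusion does not depend on which TEAE window applies: with 10 days, completers have none.

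**What to change.** First reconcile the TEAE window, which is 3 days in Sections 2.1.4 and 2.1.4.2 and 10 days (1 day for hypoglycemia) in Section 2.5.3, since it decides which events and days count as post-treatment.

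Then add to Section 2.4.5.2, for the separate post-treatment AE table only:

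- Print by arm the number of safety-population patients who permanently stopped IMP before Visit 19 and were followed beyond the end of the TEAE period, with their total post-treatment patient-years.
- Give n (%) over that number, and the rate per patient-year.
- List any post-treatment events in completers separately.
- State that the table describes a subgroup formed after randomization and is not a randomized comparison, and give no relative risks for it.

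Keep the safety population as denominator for the TEAE and whole on-study tables.

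The cost is a few sentences and a flag derived from dates already collected. The downside is small denominators, particularly within ethnic/racial subgroups; printing n and patient-years makes that visible.
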